- Section 5.5.11 Discontinuation of study treatment: Updated language to define withdrawal of consent and clarify process of discontinuation
- Section 5.5.12 Withdrawal of Consent: Added section to clarify Withdrawal of Consent procedures
- Section 5.5.13 Lost to Follow-Up: Updated template language regarding patients lost to follow-up

[figure not shown]
- Section 5.5.14 Early Study Termination: Updated template language for clarification
- Section 6: Removed “premature” to clarify study discontinuation

Changes to specific sections of the protocol are shown in the track changes version of the protocol using ~~strike through red font for deletions~~ and red underlined for insertions.

IRB/IEC

A copy of this amended protocol will be sent to the Institutional Review Boards (IRBs), Independent Ethics Committees (IECs) and Health Authorities.

The changes described in this amended protocol require IRB/IEC approval prior to implementation. In addition, if the changes herein affect the Informed Consent, sites are required to update and submit for approval a revised Informed Consent that takes into account the changes described in this amended protocol.

Amendment 6

As of 01 March 2014, 19 patients have been enrolled under protocol Amendment 4 of the protocol. A total of 17 patients completed the 22 week core phase of the study and 2 patients were discontinued. Of the 17 patients who completed the core phase, 16 patients are enrolled in the optional long term extension-1 of the study.

Amendment Rationale

The purpose of this protocol amendment is to continue the study to monitor patients for long-term safety and efficacy, and to provide continued access to LCI699 to patients who have completed long term extension-1. As there are only 16 patients currently participating in extension-1, and the clinical development program of LCI699 is still in its early stage, it is important to continue to collect long-term safety and efficacy data over a longer period of time. In addition, considering that currently available alternative treatment options have limitations to their efficacy and safety profiles, this additional extension (extension-2) will provide patients who are clinically benefitting from LCI699 an opportunity to continue to have access to the drug until LCI699 is commercially available and reimbursed or through the availability of a local access program.

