#### 3.2 Secondary objectives

- To assess the 10-week safety and tolerability of multiple doses of LCI699 in patients with Cushing's disease; not specifically included in the Final CSR
- To assess the 22-week safety and tolerability of multiple doses of LCI699 in patients with Cushing's disease; extended to cover entire study duration, and included in the Final CSR
- To assess the effect of 22-week treatment with LCI699 monotherapy on 24 hour urine free cortisol (UFC) in patients with Cushing's disease; extended to cover entire study duration, and included in the Final CSR

At each scheduled assessment, the proportion of responders ( $mUFC \leq ULN$  or  $\geq 50\%$  decrease from baseline) will be presented.

In addition, the proportion of patients classified as either controlled or partially controlled will be determined as follows:

- Controlled UFC: defined as a mean of UFC level  $\leq ULN$
- Partially controlled UFC: defined as a mean of UFC level  $> ULN$  but with  $\geq 50\%$  reduction from baseline
- To assess the effect of LCI699 on steroid hormones of Hypothalamic Pituitary Adrenal (HPA)-axis in plasma, urine and saliva; included in the Final CSR
- To assess the effects of LCI699 on improving the metabolic abnormalities (hypertension, dyslipidaemia, obesity, insulin sensitivity, glycosylated hemoglobin (HbA1c) and fasting plasma glucose (FPG)) of Cushing's disease; included in the Final CSR
- To assess the steady state pharmacokinetics of LCI699 in patients with Cushing's disease; not included in the Final CSR
- To assess escape. Escape is defined as loss of UFC control (i.e.  $UFC > ULN$ ) on at least 2 consecutive visits at the highest tolerated dose after previously attaining UFC normalization; included in the Final CSR

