## **7.2 Study medication**

### **7.2.1 Exposure to Study Treatment**

The duration of exposure to the study drug will be summarized by descriptive statistics using the SAS.

Duration of exposure is calculated as

Duration of exposure (weeks) = (min (date of last administration of LCI699, date of data cut-off) – date of first administration of LCI699 + 1)/7

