### 7.5.1.3 General rules for AE reporting

AE summaries will include all AEs starting on or after study day 1 (i.e. on or after the day of the first administration of study drug) and ending no later than 28 days after last study treatment or the follow-up visit, whichever is later. All AEs before data cutoff date will be listed, including those that start before study day 1. AEs starting prior to study day 1 will be identifiable based on the AE start date displayed in the listings.

AEs will be summarized by presenting the number and percentage of patients having at least one AE, and having at least one AE in each body system/primary system organ class and for each preferred term using the most current MedDRA coding available prior to database lock. A subject with multiple occurrences of an AE will be counted only once in the AE category. Separate AE summaries will be presented by primary system organ class, preferred term, and maximum CTC grade. A patient with multiple CTC grades for an AE will be summarized under the maximum CTC grade recorded for the event. In the summaries presented by grade, all AEs will be pooled regardless of whether they are CTC gradable or not. AEs with missing CTC grade will be summarized under “missing”.

Any information collected (e.g. CTC grades, relationship to study drug, action taken etc.) will be listed as appropriate.

For the legal requirements of ClinicalTrials.gov and EudraCT, two required tables on on-treatment adverse events which are not serious adverse events with an incidence greater than 5% and on-treatment serious adverse events and SAE suspected to be related to study treatment will be provided by system organ class and preferred term on the safety set population.

If for the same patient, several consecutive AEs (irrespective of study treatment causality, seriousness and severity) occurred with the same SOC and PT:

- a single occurrence will be counted if there is  $\leq 1$  day gap between the end date of the preceding AE and the start date of the consecutive AE
- more than one occurrence will be counted if there is  $> 1$  day gap between the end date of the preceding AE and the start date of the consecutive AE

For occurrence, the presence of at least one SAE / SAE suspected to be related to study treatment / non SAE has to be checked in a block e.g., among AE's in a  $\leq 1$  day gap block, if at least one SAE is occurring, then one occurrence is calculated for that SAE.

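### Adverse-event incidence is tabulated only as the percentage of patients ever affected over the whole study, with no phase-specific denominator or patient-time rate, although exposure runs from under 22 weeks to more than 4.5 years

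*SAP*

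**What the plan says.** SAP section 3 makes long-term safety and efficacy the focus of the Final CSR. In SAP 3.2 the 22-week safety objective is "extended to cover entire study duration, and included in the Final CSR".

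The AE rules are in SAP 7.5.1.3:

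- Measure: "AEs will be summarized by presenting the number and percentage of patients having at least one AE", overall, by system organ class and preferred term, and by maximum grade.
- Counting: "A subject with multiple occurrences of an AE will be counted only once in the AE category".
- Window: from study day 1, "ending no later than 28 days after last study treatment or the follow-up visit, whichever is later". Its length therefore differs from patient to patient.
- Registry disclosure tables: "more than one occurrence will be counted if there is" a gap of more than one day. This counts repeat events but brings in no patient-time.

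SAP 7.5.1.4 defines groupings of special interest and names no statistic for them. SAP 7.2.1 treats exposure separately: "The duration of exposure to the study drug will be summarized by descriptive statistics using the SAS". It is not linked to the AE tables.

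Neither document plans a patient-year rate, a time-to-first-AE analysis or an AE table by study phase. SAP section 6 shows the core PoC follow-up cohort and the expansion cohort separately, with an All Patients column.

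**The concern.** The percentage of patients ever having an event is a cumulative quantity. When some patients contribute weeks and others years, it has three weaknesses.

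1. It rises with follow-up even when risk is constant, so a whole-study percentage cannot be set beside a 22-week one.
2. It merges titration-phase events with events that emerge after years. Protocol 3.5 says sex-steroid increases must be watched long-term, and the Amendment 4 rationale cites longer-term safety, so timing matters here.
3. Patients who left early stay in the denominator for late events they were no longer observed to have, which understates late-onset incidence.

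The SAP deals with unequal follow-up elsewhere. Response denominators are redefined after the core phase (7.3.2.1), escape uses Kaplan-Meier with censoring (7.3.2.4), and protocol deviations are counted by Week 22 and by the end of extension (7.1.6). AE incidence has no counterpart.

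**Working it through.** The plan states no event rate or precision figure for AEs, so there is nothing to reproduce. The check has three parts.

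**1. How unequal is exposure?** Inputs are the patient counts in the protocol's amendment rationales.

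- 01 March 2014 (Amendment 6), 19 patients enrolled: "A total of 17 patients completed the 22 week core phase of the study and 2 patients were discontinued". Then: "Of the 17 patients who completed the core phase, 16 patients are enrolled in the optional long term extension-1 of the study".
- Ongoing later: 12 on 30 November 2015, 11 on 14 June 2017, 10 on 03 May 2018 (Amendments 7, 8 and 9).

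All 17 core completers had reached Day 154 by 01 March 2014, so the latest possible first dose among them is about 28 September 2013. From then to 03 May 2018 is 1,678 days = 4.59 years (240 weeks), the minimum for the 10 ongoing patients. The two who stopped in the core phase had under 154 days (0.42 years). The ratio is at least 1,678 / 154 = 10.9. The ceiling, from Amendment 4 (26 March 2012) to 31 December 2019, is 7.8 years.

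Guaranteed patient-time to 03 May 2018:

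| Patients | Minimum years each | Total |
|---|---|---|
| 10 ongoing May 2018 | 4.59 | 45.9 |
| 1 ongoing June 2017, not May 2018 | 3.71 | 3.7 |
| 1 ongoing November 2015, not June 2017 | 2.17 | 2.2 |
| 4 entered Extension-1, left by November 2015 | 0.42 | 1.7 |
| 1 completed core only | 0.42 | 0.4 |
| 2 stopped in core | 0 | 0 |
| **19** | | **53.9** |

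The 10 long-stayers supply 45.9 / 53.9 = 85% of this minimum. Their share of actual patient-time is not known. Dose interruptions and the ±2-day visit window are ignored.

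**2. What does that do to a crude percentage?** Assume a constant hazard and a 22-week incidence p. Neither comes from the documents. Then rate = −ln(1 − p) / 0.4216 per year, and incidence by time t = 1 − exp(−rate × t).

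| Assumed p at 22 weeks | Per 100 patient-years | At 70 weeks | At 4.59 years | Expected in the 19-patient table |
|---|---|---|---|---|
| 5% | 12.2 | 15.1% | 42.8% | 27% |
| 10% | 25.0 | 28.5% | 68.3% | 44% |
| 20% | 52.9 | 50.8% | 91.2% | 61% |

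The last column averages over the minimum exposures in part 1. For p = 10%: (10 × 0.683 + 0.604 + 0.419 + 5 × 0.10 + 2 × 0) / 19 = 8.35 / 19 = 44%. The patient-year rate is the same at every follow-up length; the percentage is not.

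**3. Dilution of late events.** Suppose 3 patients have an event that first appears in Extension-2. The whole-study table shows 3/19 = 16%. The number who entered Extension-2 is not stated, but lies between 12 (ongoing there in November 2015) and 16 (entered Extension-1). Among patients who could have had the event, the figure is 3/16 = 19% to 3/12 = 25%.

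**The case against.** The strongest reply is that this is a small, exploratory, single-arm study with descriptive safety analysis, and no decision rule depends on an AE percentage. AE information is displayed by patient, and the listings show start dates. Laboratory results are reported at each visit through the extensions, and ECG is summarised by visit with change from baseline. With about 19 patients, a careful reader can see from the listings whether events came early or late. All of that stands. A reader might infer that safety as a whole is reported only as crude percentages; it is not. The gap is confined to the AE incidence summaries, and none of these other outputs adjusts them for exposure.

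A reader might also infer that the two cohorts cannot be compared. The documents do not show that. They give neither the size of the follow-up cohort nor exposure by cohort, the core visit schedules are similar, and no formal comparison is planned. At the 10% hazard above, assumed follow-up of 2 versus 4 years would give 39% versus 63%; equal follow-up would give no distortion. The columns are interpretable if exposure is similar, but the plan has no safeguard if it is not.

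Nor does the SAP plan to compare AE percentages with earlier CSRs. The point is only that such a reading would be invalid.

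Finally, a constant hazard is doubtful. Symptoms suggestive of cortisol withdrawal occurred during the 10-week PoC treatment, and front-loaded events would inflate the percentages less than the table suggests. That is a fair limit on the illustration, and also a reason to show events by phase.

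**Conclusion.** The point holds as a limited weakness in the AE incidence summaries. The tables would be correct as percentages ever affected, but they cannot separate early from late or accumulating events, they dilute late-onset incidence, and they cannot be read against 22-week figures.

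The exposure spread is firm: under 22 weeks for 2 of 19 patients, and at least about 4.6 years for 10 of 19. It follows from the protocol's counts and dates. The rise from 10% to 68% (43% to 91% for 5% to 20% at week 22) rests on an assumed constant hazard; it shows the mechanism and does not estimate bias in this trial. No efficacy result or study conclusion is invalidated. The change would improve the answer to a stated safety objective, using data already collected.

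**What to change.** Keep n (%) as planned. In SAP 7.5.1.3 and 7.5.1.4 add the following for overall AEs, SAEs and each special-interest group:

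- **(a) By phase.** n (%) for core, Extension-1 and Extension-2. The denominator is the number of patients entering that phase, and any event starting in the phase counts, whether or not the patient had one earlier.
- **(b) Patient-time.** First-event incidence per 100 patient-years with exact 95% CI, for each cohort and All Patients. Person-time runs from Day 1 to the earliest of first event, end of the 7.5.1.3 AE window, or last in-study contact. For patients entering the roll-over study, last contact is the EOT visit, because they have no EOS visit. A flat 28 days added for everyone would not fit them.

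First and last dose dates and AE start dates are already used in SAP 7.2.1 and 7.5.1.3, so no new data are needed. The cost is a few extra tables. Restricting them to these categories avoids many near-empty preferred-term cells. Rates will be imprecise at about 19 patients, which the intervals will show. A single rate in (b) assumes constant hazard, which (a) helps to check.

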#### **7.5.1.4 Adverse events of special interest / grouping of AEs**

Groupings of AEs of special interest consist of adverse events for which there is a specific clinical interest in connection with osilodrostat treatment (i.e. where osilodrostat may influence a common mechanism of action responsible for triggering them) or adverse events which are similar in nature (although not identical).

An Excel file with the exact composition of the adverse events groupings is available in the CREDI folder “/CREDI Projects/L/LCI699C/Administrative files/CIS (Clinical Information Sciences)/Biostatistics” which is to be used to map reported adverse events to the adverse events groupings. This file is updated periodically after MedDRA update and/or review of accumulating trial data. Prior to database lock, the file will be copied to proper CREDI study specific folder such as RAP folder.

#### **7.5.2 Laboratory abnormalities**

For analyzing laboratory results, data from all sources (central and local laboratories) will be combined. The summaries will include all laboratory assessments up to data cut-off date. All laboratory assessments will be listed. Results will be reported for each visit at which collected in the core, follow-up, and extension phases through the last study visit.

Biochemistry, hematology, and urine laboratory data, will be presented using

- shift tables using CTC grades (if available), otherwise by normal ranges: both standards from baseline to most extreme post-baseline value and baseline to last value
- listings flagging values with elevated CTC grades (i.e. greater than 0), and outside of the normal ranges otherwise

All laboratory values will be converted into SI units and the severity grade derived using NCI Common Terminology Criteria for Adverse Events (CTCAE) v4.0. Blood glucose will be presented as mg/dL and will be assessed using the ADA criteria 2010. Insulin and QUICKI may also be presented in US unit. In the unlikely case a local laboratory normal range overlaps into the higher (i.e. non-zero) CTC grade, if the laboratory value is within local normal limits it will be assigned a CTC grade of zero.

The following summaries will be produced for the laboratory data (by laboratory parameter):

- Number and percentage of patients with worst post-baseline CTC grade (regardless of the baseline status). Each patient will be counted only for the worst grade observed post-baseline
- Number and percentage of patients meeting categorical liver function test criteria, including Hy’s Law criteria for liver injury (ALT or AST > 3 x ULN and TBIL  $\geq$  2 x ULN and ALP < 2 x ULN). Each patient will be counted only for the worst grade observed post-baseline
- Shift tables using CTC grades to compare baseline to the worst post-baseline values will be produced for hematology and biochemistry laboratory parameters with CTC grades
- For laboratory parameters in which CTC grades are not defined, shift tables to the worst post-baseline values will be produced using the low/normal/high classifications based on laboratory reference ranges
- Selected laboratory data will be also be displayed by presenting summary statistics of change from baseline values.

The following listings will be produced for the laboratory data:

- Listing of all laboratory data with values flagged to show the corresponding CTC grades and/or ADA classifications (normal/impaired/diabetic) and the classifications relative to the laboratory reference ranges
- Listing of notable laboratory abnormalities (i.e. newly occurring CTC grade 3 or 4 laboratory toxicities).

### 7.5.3 Vital signs

All vital signs data (height (cm), weight (kg), body temperature ( $^{\circ}$ C), sitting pulse rate (bpm), systolic/diastolic blood pressure (mmHg)) will be listed by patient and visit/time, and abnormalities will be flagged on listing. Shift table based on notable value will be provided for vital signs. For blood pressure, we will provide the mean of the 3 measurements.

The criteria for clinically notable abnormalities are defined as follows:

#### 7.5.3.1 Clinically notable elevated values

- Systolic BP:  $\geq 180$  mmHg and an increase  $\geq 20$  mmHg from baseline
- Diastolic BP:  $\geq 105$  mmHg and an increase  $\geq 15$  mmHg from baseline.
- Supine pulse:  $\geq 120$  bpm with increase from baseline  $\geq 15$  bpm

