3.5 Risk/ benefit for this study

Potential benefits

Biochemical remission is a goal in the treatment of Cushing's disease. Preliminary data from this PoC study in patients with Cushing's disease clearly demonstrated that LCI699 can reduce and normalize plasma cortisol in this population. However, it is unknown whether patients responding to LCI699 will eventually loose UFC control. Patients will be discontinued from LCI699 treatment in case of unsatisfactory response.

The primary treatment and standard of care for Cushing's disease is surgical removal of the pituitary tumor via transsphenoidal adenectomy. Therefore, in order to avoid any potential delay in receiving first line treatment patients enrolled under [Amendment 4](#) should have either failed standard therapy (including surgery) or can be de novo patients for whom surgery is not an option. Given LCI699's potency to suppress cortisol synthesis, it is conceivable that patients may ameliorate some of the sequelae of their hypercortisolism state while on the drug for the planned duration of this study protocol following [Amendment 4](#). Patients who are responding to LCI699 with good tolerability have the option to participate in optional two long term extension phases of the study.

Potential risks

Based on the preclinical and clinical experience with LCI699 the risks associated with this study are outlined below. The risks to patients will be minimized by strict inclusion/exclusion criteria, close clinical monitoring and predefined dose adjustment and dose termination criteria (see [Section 5.5.4](#) and [Section 5.5.9](#)).

Effects on QTc interval

Final results from the completed ICH E14-compliant thorough QT Study LCI699C2105 showed that the predicted mean QT effect of osilodrostat was below the threshold of regulatory concern for the currently investigated dose range (2-30 mg twice a day [bid]).

Effects on blood pressure

LCI699 has been shown to reduce BP of hypertensive patients in a dose dependent manner over 4-8 weeks. An acute decrease in BP has not been observed with LCI699 in healthy volunteers (up to 200 mg) or hypertensive patients (range tested = 0.25 mg - 2 mg/day). Doses used in this study will be higher than those where a BP effect was observed, and may therefore elicit larger decreases in BP than observed to-date. Patients with Cushing's disease have a high prevalence of hypertension and effective treatment of hypercortisolism may result in reductions in blood pressure.

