5.5.6 Follow up on potential drug-induced liver injury (DILI) cases

Patients with transaminase increase combined with TBIL increase may be indicative of potential DILI, and should be considered as clinically important events.

The threshold for potential DILI may depend on the patient's baseline AST/ALT and TBIL value; patients meeting any of the following criteria will require further follow-up as outlined below:

- For patients with normal ALT and AST and TBIL value at baseline: AST or ALT > 3.0 x ULN combined with TBIL > 2.0 x ULN
- For patients with elevated AST or ALT or TBIL value at baseline: [AST or ALT > 2 x baseline AND > 3.0 x ULN] OR [AST or ALT > 8.0 x ULN], combined with [TBIL > 2 x baseline AND > 2.0 x ULN]

Medical review needs to ensure that liver test elevations are not caused by cholestasis, defined as ALP elevation > 2.0 x ULN with R value < 2.

Note: (The R value is calculated by dividing the ALT by the ALP, using multiples of the ULN for both values. It denotes whether the relative pattern of ALT and/or ALP elevation is due to cholestatic ($R \leq 2$), hepatocellular ($R \geq 5$), or mixed ($R > 2$ and < 5) liver injury).

In the absence of cholestasis, these patients should be immediately discontinued from study drug treatment, and repeat LFT testing as soon as possible, preferably within 48 hours from the awareness of the abnormal results. The evaluation should include laboratory tests, detailed history, physical assessment and the possibility of liver lesions, obstructions/compressions, etc.

- Laboratory tests should include ALT, AST, albumin, creatine kinase, total bilirubin, direct and indirect bilirubin, GGT, prothrombin time (PT)/ international normalized ratio (INR) and alkaline phosphatase.
- A detailed history, including relevant information, such as review of ethanol, concomitant medications, herbal remedies, supplement consumption, history of any pre-existing liver conditions or risk factors, should be collected.
- Further testing for acute hepatitis A, B, C or E infection and liver imaging (e.g. biliary tract) may be warranted.
- Additional testing for other hepatotropic viral infection (CMV, EBV or HSV), autoimmune hepatitis or liver biopsy may be considered as clinically indicated or after consultation with specialist/hepatologist.

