5.5.11 Discontinuation of study treatment

Patients may voluntarily discontinue from the study treatment for any reason at any time. If a patient decides to discontinue from the study treatment, the investigator should make a reasonable effort (e.g. telephone, email, letter) to determine the primary reason for this decision and record this information in the patient's chart and on the appropriate CRF pages. They may be considered withdrawn if they state an intention to withdraw, fail to return for visits, or become lost to follow-up for any other reason.

The investigator should discontinue study treatment for a given patient if he/she believes that continuation would be detrimental to the patient's well-being.

Study treatment must be discontinued under the following circumstances and according to Investigator discretion:

- Withdrawal of informed consent.
- Emergence of the following adverse events (compound specific):
 - hypertension defined as office mean sitting systolic BP > 180 mmHg or mean sitting diastolic BP > 110 mmHg (confirmed and persistent*).
- Any of the following laboratory abnormalities:
 - hyperkalemia (serum potassium > 5.5 mmol/L; confirmed and persistent*).
 - hypokalemia (serum potassium < 3.5 mmol/L; confirmed and persistent*).
 - hyponatremia (serum sodium < 130 mmol/L; confirmed and persistent*).
- QTcF > 500 msec, if confirmed by a cardiologist (see [Section 6.6.5](#)).
- QTcF > 480 msec, if the investigator determines it is no longer safe for the patient to continue in the study, based on ECGs, cardiac examination, and recommendation from a cardiologist (see [Section 6.6.5](#)).
- Pregnancy.
- Use of any other therapy for Cushing's disease.
- Any other protocol deviation that results in a significant risk to the patient's safety.

* Persistent is defined as unresolved with LCI699 dose or other concomitant medication changes

Patients who discontinue study treatment should NOT be considered withdrawn from the study. They should return for the assessments indicated in [Section 6](#). If they fail to return to return for these assessments for unknown reasons, reasonable effort (e.g. telephone, email, letter) should be made to contact them as specified in [Section 5.5.13](#).

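### The SAP's change-based blood pressure flag and its Hy's Law row leave out some patients who are at the protocol's own blood pressure and liver-injury thresholds

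*SAP*

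**What the plan says.** **Blood pressure.** SAP 7.5.3.1 defines a clinically notable high systolic value as "Systolic BP: $\geq 180$ mmHg and an increase $\geq 20$ mmHg from baseline". The diastolic rule has the same form: at least 105 mmHg and a rise of at least 15 mmHg. SAP 7.5.3 builds a shift table on notable values and flags abnormalities in the listing.

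Protocol 5.5.11 lists, among the circumstances for stopping treatment, "hypertension defined as office mean sitting systolic BP > 180 mmHg or mean sitting diastolic BP > 110 mmHg", if confirmed and persistent. It sets no change-from-baseline condition. The list is introduced by "Study treatment must be discontinued under the following circumstances and according to Investigator discretion".

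**Liver.** SAP 7.5.2 counts patients meeting categorical liver test criteria. These include Hy's Law "criteria for liver injury (ALT or AST > 3 x ULN and TBIL" at least 2 x ULN, with ALP below 2 x ULN.

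For normal baselines, Protocol 5.5.6 treats AST or ALT above 3 x ULN with bilirubin above 2 x ULN as potential drug-induced liver injury. It then adds: "Medical review needs to ensure that liver test elevations are not caused by cholestasis, defined as ALP elevation > 2.0 x ULN with R value" below 2. R is ALT divided by ALP, each in multiples of ULN. A separate criterion applies when baseline liver values are elevated.

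**Pulse.** SAP 7.5.3.1 and 7.5.3.2 set limits for supine pulse. SAP 7.5.3 lists sitting pulse, and Protocol 6.6.2 takes vital signs seated.

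**The concern.** Protocol 3.5 says that patients with Cushing's disease "have a high prevalence of hypertension". It also names accumulation of 11-deoxycorticosterone as a way in which the drug could raise blood pressure. A flag that requires a rise as well as a level is least sensitive in patients who start high, and they have the least room before the protocol level.

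Read literally, a criterion that needs a change from baseline cannot be met at baseline. A patient at 185 mmHg systolic throughout would be not notable at both ends of the shift table.

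SAP 3 says the Final CSR will concentrate on long-term safety and efficacy. Yet no summary table specified in the SAP counts patients who reach the protocol's blood pressure level or meet its liver-injury criteria. Listings hold the values but do not give a rate. A reader could find a hypertension discontinuation in the disposition table and no notable elevations in the shift table, with nothing to connect them.

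**Working it through.** There is no sample size or power figure to reproduce. The check sets the threshold rules side by side and looks for values that meet one and not the other.

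**Blood pressure inputs.** Protocol 5.5.11: systolic > 180 or diastolic > 110. SAP 7.5.3.1: systolic ≥ 180 with rise ≥ 20; diastolic ≥ 105 with rise ≥ 15.

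On level alone the SAP is the wider rule, so only the rise condition can cause a miss:
- Systolic is missed when 180 < value < baseline + 20, which needs baseline > 160.
- Diastolic is missed when 110 < value < baseline + 15, which needs baseline > 95.

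With whole numbers, the lowest systolic above the level is 181 and the largest unflagged rise is 19, so the gap starts at 181 − 19 = 162. For diastolic it starts at 111 − 14 = 97. The SAP uses the mean of three readings, so fractional means can bring the start slightly lower.

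| Baseline | On treatment | Rise | At protocol level | SAP systolic flag | SAP diastolic flag |
|---|---|---|---|---|---|
| 165/100 | 183/104 | 18/4 | yes | no | no |
| 150/98 | 170/112 | 20/14 | yes | no | no |
| 150/90 | 184/100 | 34/10 | yes | yes | no |
| 150/85 | 170/106 | 20/21 | no | no | yes |

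The first two rows are misses. In the third the rules agree. In the fourth the SAP flags a patient who is below the protocol level.

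Such baselines are not ruled out at entry. Protocol 4.2 has no blood pressure exclusion. Protocol 6.6.2 refers to qualifying ranges given above, but none appears in the text.

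**Liver inputs** (multiples of ULN, normal baseline). Protocol 5.5.6: ALT or AST > 3, bilirubin > 2, unless ALP > 2 and R < 2. SAP 7.5.2: ALT or AST > 3, bilirubin ≥ 2, ALP < 2.

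| ALT | Bilirubin | ALP | R = ALT/ALP | Protocol 5.5.6 | SAP Hy's Law |
|---|---|---|---|---|---|
| 9 | 2.5 | 3 | 3.0 | yes | no |
| 6 | 2.5 | 2.5 | 2.4 | yes | no |
| 4 | 2.5 | 1.5 | 2.7 | yes | yes |
| 4 | 2.5 | 2.5 | 1.6 | no | no |

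With ALP above 2, a miss needs R ≥ 2, hence ALT ≥ 2 × ALP > 4 x ULN. At ALP exactly 2 the SAP row fails and the protocol's cholestasis exemption does not apply, so that case is missed too.

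**Elevated baseline.** Protocol 5.5.6 then requires AST or ALT > 2 x baseline and > 3 x ULN (or > 8 x ULN), with bilirubin > 2 x baseline and > 2 x ULN. Entry is possible with ALT or AST up to 3 x ULN and bilirubin up to 2 x ULN (Protocol 4.2, criterion 17). Anyone meeting this version already has transaminases > 3 and bilirubin > 2 x ULN, so the SAP row misses them only through the ALP condition. The difference also runs the other way. With baseline ALT at 2 x ULN, an on-treatment ALT of 3.5 x ULN is below 2 × 2 = 4, so it does not meet the protocol criterion but does meet the SAP transaminase condition.

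**Pulse.** Protocol 5.5.11 has no pulse criterion, so there is no stopping rule to compare.

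**The case against.** Reporting flags need not equal stopping rules. A stopping rule protects an individual, whereas a level-plus-change flag describes change on treatment. The SAP uses the same design for PR, QRS and heart rate. It is also wider than the protocol on absolute level and needs no confirmation or persistence, so it can flag patients whom the protocol would not stop. All of this stands, and it means that neither rule is wrong in itself.

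A reader might infer that patients taken off drug are reported as having had no abnormality. The documents do not support that:
- A single reading of 184 mmHg does not stop treatment. The protocol treats the hypertension as an emergent adverse event, requires it to be confirmed and unresolved after dose or co-medication changes, and refers to investigator discretion.
- Hypertension that does stop treatment enters the adverse event tables, and the disposition table gives reasons for ending treatment.
- Confirmed potential liver injury with no other cause is a serious adverse event (Protocol 5.5.6), and serious events are tabulated (SAP 7.5.1.3).
- All vital signs and laboratory data are listed. Change in blood pressure is summarised over time, and CTC-grade tables cover the laboratory data.

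Hy's Law is also not a notable flag. SAP 7.5.2 reserves that term for newly occurring CTC grade 3 or 4 results, and Hy's Law is only one of its categorical liver criteria.

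Two further points limit the practical weight. Preliminary data showed mean blood pressure falling by 13.1/9.3 mmHg at Day 70 (Protocol 1.1.1.3). The liver criteria came with Amendment 7, when 12 patients were ongoing and no suspected case was known.

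What remains is that a listing or an event term does not give the number of patients who reached a stated threshold, and no specified table does.

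**Conclusion.** The point holds as a reporting gap. In patients with high baseline pressure, the vital-signs shift table and flagged listing can show no notable elevation while the patient is at the protocol's absolute level. The Hy's Law row can omit patients who meet Protocol 5.5.6 with ALP at or above 2 x ULN and R at or above 2.

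The consequence is limited to those summary counts. The number of patients affected cannot be computed, because the documents give no distribution of baseline blood pressure or liver tests. For scale only, and assuming one missed patient in the blood pressure table, the rate would move by 1/15 = 6.7 percentage points in an expansion cohort of 15, or 1/19 = 5.3 points among the 19 patients enrolled under Amendment 4.

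Two stronger readings should not be drawn. There is no mismatch with a pulse stopping rule, because the protocol has none; supine is a labelling slip. The lack of an elevated-baseline version does not by itself make the Hy's Law row an undercount, since that difference can add patients to the row.

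The conclusion assumes that the SAP flags are programmed as written and that high baselines can occur, which the entry criteria do not prevent.

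**What to change.** - **SAP 7.5.3:** beside the existing flag, add the number and percentage of patients with mean sitting systolic above 180 or diastolic above 110 mmHg at any post-baseline visit, regardless of change from baseline.
- **SAP 7.5.2:** beside the Hy's Law row, add a row for patients meeting the laboratory criteria of Protocol 5.5.6, with the R-value exclusion for cholestasis and the elevated-baseline version.
- **SAP 7.5.3.1 and 7.5.3.2:** change supine pulse to sitting pulse, as a labelling correction only.

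The cost is a few table rows and some programming on data already collected. The reported counts may look slightly less favourable. The existing flags stay, and no clinical rule changes.
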